*Hypothesis: Improved glycemic control can be attained with lower total daily insulin requirements in subjects treated with liraglutide.* Total daily insulin dose will be determined for seven days before and after initiation of liraglutide therapy. Insulin dose/kilogram body weight will be determined and evaluated in relationship to changes in mean weekly blood sugars.

In addition to the specific aims outlined above, the following exploratory aims will be addressed:

**Exploratory Aim 1:** Determine the side effect profile of liraglutide in adolescents/young adults with T1DM. *Hypothesis: Side effect profile of short-term liraglutide treatment in this population will be similar to that reported in adults.* Study subjects will keep a diary reporting hypoglycemic events and other potential adverse effects. Type, number, and rate of adverse events will be determined.

**Exploratory Aim 2:** Determine if there is a difference in caloric intake with liraglutide treatment in adolescents/young adults with T1DM. *Hypothesis: Caloric intake decreases in response to liraglutide treatment.* Subjects will keep a 4 day food record before and after initiation of liraglutide. Total caloric intake will be calculated, and within subject differences in caloric intake before and after liraglutide treatment will be determined.

**Exploratory Aim 3:** Determine if liraglutide treatment alters serum inflammatory markers in subjects with T1DM. *Hypothesis: Acute liraglutide therapy decreases serum levels of C-reactive protein and increases adiponectin levels in subjects with T1DM.* Serum samples before and after liraglutide therapy will be drawn and levels of inflammatory markers will be measured. Within subject differences will be determined.

Describe any relevant preliminary data.

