#### **Visit 3**

- Insulin pump settings
- Total daily insulin dose
- Food diaries
- Download of continuous glucose monitor – mean weekly blood sugars
- Blood sugar records with reports of hypoglycemia
- Adverse effects
- Mean blood glucose excursion, glucagon release, and serum inflammatory markers during mixed meal tolerance test

*Describe any primary or secondary safety endpoints.*

**Response:** Adverse effects including nausea/vomiting, anorexia. Injection site reactions/pain. Rates of hypoglycemia. Clinical or biochemical evidence of pancreatitis.

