## **8.0 Procedures Involved**

### *8.1 Describe and explain the study design.*

**Response:** This is a pilot unblinded prospective within subject investigational-drug intervention trial.

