#### **Visit 1 Screening Day (day 0):**

- Review the subject's medical history and family medical history
- Review subject's blood sugars and insulin pump settings
- Measure height, weight, blood pressure and heart rate.
- The principal investigator will perform a physical exam.
- If hemoglobin A1c level is not recorded in the medical record within 2 weeks of visit 1, this test will be performed.
- Record mean total daily insulin dose (previous 72 hours) from insulin pump.
- Subjects will be advised to wear his/her continuous glucose monitor (CGM) for the next two weeks, changing sites as indicated by the manufacturer.
- For subjects who do not have a CGM, we will insert the Abbott Freestyle Libre Professional Device. This device will monitor glucose levels throughout the entire study period. Subjects will be advised to check blood sugars at least 4 times per day and at any occasion when symptoms of hypoglycemia develop.
- Subjects will be asked to keep a record of any episodes of hypoglycemia.
- Subjects will be asked to keep a 4 day food record (three days, 1 weekend day).
- Subjects will be advised to follow their usual diabetes care plan with respect to carbohydrate counting, diet and exercise.

**Visit 2 (Day 7):** Subjects will come fasting for this visit. They will bring the food records and diary of hypoglycemia to this visit. This visit will take approximately 4 hours. At this visit, the following procedures will be performed:

- Records of blood sugars and CGM data will be obtained from subjects wearing personal CGMs
- Subjects wearing the Freestyle LibrePro system will continue wearing the device unless it became dislodged during the study. A new device will be placed in this case.
- Blood sugars and insulin pump settings will be reviewed.
- Record mean total daily insulin dose (previous 72 hours) from insulin pump.
- A Mixed Meal Tolerance test will be performed (see below)

- Insulin pump settings will be adjusted to decrease the risk of hypoglycemia during liraglutide treatment. Basal rates will be decreased by 25% and meal boluses will be decreased by 33%.
- The first dose of liraglutide will be given at the study site. Subjects will be given 0.6 mg subcutaneously. Subjects will be taught how to use the delivery device at this visit.
- Subjects will be advised to take 0.6 mg of liraglutide subcutaneously every morning at about the same time.

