- Subjects will be given a diary and be asked to record any episodes of hypoglycemia, as well as any other side effects such as nausea, decrease in appetite, and other problems.
- Subjects will be asked to keep a 4 day food record (three days, 1 weekend day).
- Subjects will be provided with contact information for the principal investigator in case of any problem or untoward side effect. They will be asked to notify the study staff for persistent low blood sugar (BS < 70 mg/dL), persistent high blood sugar (BS > 250 mg/dL), or urine ketones.
- Subjects will be advised to return to clinic in 7 days.

**Visit 3 (Day 14):** This is the final study visit. Subjects will come fasting for this visit. The subject will not take liraglutide prior to coming to this visit but will bring the study drug to the visit. Subjects will bring the food records and diary of hypoglycemia to this visit. This visit will take approximately 4 hours. At this visit, the following procedures will be performed:

- Records of blood sugars and CGM data will be obtained.
- Freestyle LibrePro device will be removed and data obtained.
- Blood sugars and insulin pump settings will be reviewed
- Record mean total daily insulin dose (previous 72 hours) from insulin pump.
- Liraglutide (0.6 mg subcutaneously) will be administered 45 minutes prior to the Mixed Meal Tolerance Test
- A Mixed Meal Tolerance test will be performed (see below).
- All study drug will be returned.
- Subjects will be advised to resume previous basal rates and carbohydrate ratios within 48 hours of final study visit.

**Mixed Meal Tolerance Test (MMTT).** This test will be done at Visit 2 and Visit 3. The MMTT is a test to measure blood sugar levels in response to a meal and the amount of glucagon that is produced in response to changes in blood sugar. Prior to the test, a catheter will be placed to reduce the number of needle sticks during the test. Subjects will drink 240 ml of a high protein nutrition drink (BOOST). An appropriate amount of insulin for the carbohydrate intake of the meal challenge will be administered via insulin pump to taking the drink. Blood will drawn once before the meal and 8 times during the meal over 3 hours. The total amount of blood that will be drawn is ~ 20 teaspoons (100 mL).

The following parameters will be drawn for measurement during the MMTT

- Blood Glucose
- Glucagon
- Serum inflammatory mediators

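### Nausea, vomiting, reduced appetite and other general symptoms are prompted only in the treated week, so their on-treatment rates have no own-baseline rate

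*Combined protocol and SAP*

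**What the plan says.** Section 8.1 gives the design: "This is a pilot unblinded prospective within subject investigational-drug intervention trial". Each subject has seven untreated days (Visit 1 to Visit 2) and then seven treated days (Visit 2 to Visit 3).

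For the untreated week, the Visit 1 list in section 8.2 says "Subjects will be asked to keep a record of any episodes of hypoglycemia" and adds a food record. At Visit 2, "They will bring the food records and diary of hypoglycemia to this visit". No other subject-reported record is mentioned for that week.

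At Visit 2, when liraglutide starts, subjects receive a diary for hypoglycemia "as well as any other side effects such as nausea, decrease in appetite, and other problems". The variables lists in section 7.1 agree with this: adverse effects appear under Visit 3 and not under Visit 1 or Visit 2.

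The safety endpoints at the end of section 7.1 begin with "Adverse effects including nausea/vomiting, anorexia". Exploratory Aim 1 (section 1.3) hypothesises "Side effect profile of short-term liraglutide treatment in this population will be similar to that reported in adults" and says "Type, number, and rate of adverse events will be determined".

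**The concern.** The trial has no parallel control group, so the untreated week is its only internal control. The plan uses that week for CGM glucose, insulin dose, food intake, the meal test and inflammatory markers. General symptoms are the exception, and no reason is given.

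Subjects are told what side effects to expect, know when they are on the drug, and are asked about named symptoms only from that point. A report of nausea in the treated week may then reflect the drug, a symptom the subject had anyway, or the prompt itself. The data cannot tell these apart. Section 14.1 says the results may be used to develop longer placebo-controlled studies, so a symptom rate that includes background could be carried into their planning.

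**Working it through.** **1. The two weeks side by side** (sections 7.1 and 8.2)

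| Item | Untreated week | Treated week |
|---|---|---|
| Hypoglycemia episodes | recorded by subject | recorded by subject |
| CGM | worn | worn |
| 4-day food record | kept | kept |
| Nausea, appetite, other problems | not asked for | asked for in diary |
| Adverse effects in the variables lists | not under Visit 1 or 2 | under Visit 3 |

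Two other places could be read as supplying a baseline. Section 8.5 lists a side effect diary among the source records but gives no timing. Section 13.1 says side effects will be monitored during the study but describes no pre-dose recording. Neither changes the table.

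**2. The plan's own figure.** The documents give no figure for tolerability. The only sample-size figure is in section 10.2: 9 subjects for a change of 22 ± 20 mg/dL, 80% power, alpha 0.05, paired t-test. Reading 20 as the SD of the paired difference, d = 22/20 = 1.1. Two-sided power from the noncentral t distribution (n − 1 degrees of freedom, noncentrality d√n) is 76.1% at n = 8, 82.3% at n = 9 and 93.3% at n = 12. The stated 9 is reproduced, and nothing in this point alters it.

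**3. What treated-week data alone can show.** Suppose 3 of the maximum 12 subjects report nausea on treatment. This count is an assumption, since the documents give no rate. The proportion is 3/12 = 25%, with an exact (Clopper-Pearson) 95% interval of 5.5% to 57.2%. For 0/12 the interval is 0% to 26.5%. These widths come from the sample size and would be the same with a baseline diary, so they do not measure the gap.

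The gap is one of identification. Let a be the number of subjects with the symptom in both weeks, b in the treated week only, and c in the untreated week only. The plan observes only a + b. With a + b = 3, b can be 0, 1, 2 or 3, so the proportion with a new symptom can lie anywhere from 0/12 = 0% to 3/12 = 25%. Nothing is known about c, so the within-subject difference (b − c)/12 cannot be estimated.

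**4. What a baseline diary would add.** It would make a, b and c observable. For a formal test (exact McNemar), if all m discordant pairs go the same way, two-sided p = 2 × 0.5^m. Five pairs give 0.0625 and six give 0.031, so six are needed.

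Power at n = 12 is the sum of the trinomial probabilities of all (b, c) with exact p ≤ 0.05. When no subject has the symptom only off treatment, this reduces to P(Binomial(12, π) ≥ 6), where π is the treated-only rate. All rates below are assumptions.

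| Treated-only rate | Power, untreated-only rate 0% | Power, untreated-only rate 5% |
|---|---|---|
| 30% | 11.8% | 8.0% |
| 40% | 33.5% | 22.6% |
| 50% | 61.3% | 42.0% |

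A paired test would therefore have little power. The benefit lies in being able to report a, b and c.

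**The case against.** The strongest reply is that no planned analysis breaks. Exploratory Aim 1 promises type, number and rate of events and compares them with an adult profile, whereas Exploratory Aims 2 and 3 explicitly promise within-subject differences. That is correct. A reader might infer that Aim 1 cannot be carried out, and the documents do not support this: the counts it promises can be produced. What they cannot show is how much of a count was already there before dosing.

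A reader might also infer that hypoglycemia is captured differently in the two weeks, by a plain record first and a fuller diary later. The text does not support this. Both weeks ask subjects to record every episode, section 8.2 describes what is brought back in the same terms at Visits 2 and 3, the variables lists use one entry for both visits, and CGM covers both weeks. The added prompts concern other symptoms.

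Appetite is partly covered: "Subjects will keep a 4 day food record before and after initiation of liraglutide". The diary item is also worded as a decrease, which implies comparison with the subject's usual state. Both points stand, but a food record measures intake rather than the symptom and says nothing about nausea. Injection-site reactions to the study drug have no untreated counterpart, so no baseline is missing for them.

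Finally, the data collection tool is an attachment that is not reproduced in the document, so its contents cannot be checked here. The schedule and the variables lists nevertheless agree with each other.

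**Conclusion.** The point holds for nausea, vomiting, reduced appetite and other general symptoms. Nausea/vomiting and anorexia are the first-named safety endpoints, and all these symptoms feed Exploratory Aim 1. They are solicited in one period only, so their on-treatment rates have no own-baseline rate and cannot be separated from background. In the 3-of-12 illustration, the share of subjects with a new symptom is known only to lie between 0% and 25%.

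It does not extend to hypoglycemia, to injection-site reactions, or to any planned test. The documents state no rule for attributing events, so it would also go too far to say that background symptoms will be ascribed to liraglutide. Nor would a baseline diary isolate a drug effect. The order of periods is fixed, treatment is open-label, and insulin is reduced at the same visit that liraglutide starts. The diary would remove one avoidable ambiguity, and the result would remain descriptive. This is an inexpensive improvement worth making before enrolment, because untreated-week symptoms cannot be recovered afterwards.

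**What to change.** - Give subjects at Visit 1 the same symptom diary now first given at Visit 2, and collect it at Visit 2.
- Add symptoms to the Visit 2 variables in section 7.1.
- State in section 8.2 that the symptom diary is returned at Visit 3. The Visit 3 text names only the food records and the hypoglycemia diary.
- In section 10.1, report for each symptom the number of subjects with it in the treated week only, the untreated week only, both and neither, with exact intervals, labelled as descriptive. Report injection-site reactions for the treated week alone.

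The cost is one more copy of an existing form and a few minutes of extra recording per subject in week 1. The sample size of 9, with up to 12 enrolled, does not change.

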**Response: Types of Risk:**

**Important Safety Information (see attached product information):** In animal studies, liraglutide caused rats and mice to develop thyroid tumors, some of which were cancers. It is not known whether liraglutide causes thyroid tumors or a type of thyroid cancer called medullary thyroid cancer in humans. Subjects with a history or family history of medullary thyroid cancer or Multiple Endocrine Neoplasia syndrome type 2 (MEN2) will not be enrolled in this study.

Treatment with GLP-1 is associated with inflammation of the pancreas (pancreatitis) which may be severe and can lead to death. Certain conditions increase the risk of developing pancreatitis including history of pancreatitis, gallstones, alcoholism, or high triglyceride levels. We will review the subject's medical record to assess for any of these risk factors. In addition, subjects will be excluded if they have a history of pancreatitis. While taking liraglutide, the subjects will be counseled to notify study staff if they develop severe abdominal pain. Should this occur, they will be advised to discontinue liraglutide and testing for pancreatitis will be performed (serum amylase and lipase). Subjects will also be counseled not to consume alcohol while enrolled in this study.

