Glucagon-like peptide 1 is an incretin hormone that is released in response to ingestion of food. Long-acting GLP-1 analogues and drugs which inhibit the metabolism of GLP-1 are FDA-approved as adjuvant therapy for the treatment of Type 2 diabetes. These drugs are currently not approved for use in the T1DM population. Individuals treated with GLP-1 analogues are at increased risk for hypoglycemia. It is recommended that patients treated with insulin secretagogue therapies (ie sulfonylureas), have their secretagogue dose decrease when GLP-1 analogue therapy is initiated. In this study, subjects have T1DM and are reliant on insulin for blood sugar control. In order to decrease the risk of hypoglycemia in this population, subjects will be counseled to decrease their basal insulin rates by 25% and their bolus insulin coverage for carbohydrates by 30% during the seven days when they are receiving liraglutide. All study subjects will be advised to check their blood sugar if they experience any symptoms consistent with hypoglycemia. They will be asked to contact the study team for persistent hypoglycemia while taking liraglutide. In addition, because insulin doses will be decrease significantly when liraglutide is initiated, there is the risk that subjects will experience hyperglycemia and may develop ketonuria. Subjects will be advised to contact the study team for persistent hyperglycemia and/or presence of urine ketones. The insulin dose will be increased to address this concern.

The most common side effects experienced by adults taking liraglutide include headache, nausea, and diarrhea. Nausea is most common when first starting liraglutide but generally decreases with time. Subjects may also feel less hungry while taking liraglutide. We will monitor for these and additional side effects during the study.

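### No safety contact or data collection is scheduled after Visit 3, although a liraglutide dose is given there and subjects restore their insulin settings within the next 48 hours

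*Combined protocol and SAP*

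**What the plan says.** Section numbers follow the body of the protocol, not its table of contents.

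Section 6.1 gives three visits over two weeks. Section 8.2 says of Visit 3 (Day 14): "This is the final study visit". At that visit:

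- Dosing: "Liraglutide (0.6 mg subcutaneously) will be administered 45 minutes prior to the Mixed Meal Tolerance Test".
- For subjects on the study sensor: "Freestyle LibrePro device will be removed and data obtained".
- The hypoglycemia diary is brought in, staff review glucose and pump settings, and study drug is returned.
- On insulin: "Subjects will be advised to resume previous basal rates and carbohydrate ratios within 48 hours of final study visit".

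Section 8.6, which asks about longer follow-up, only refers back to earlier text, and none of that text goes beyond Day 14. Section 11 sets no safety window after the last dose.

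The reporting instructions are not uniform. At Visit 2, section 8.2 gives contact details for any problem and adds: "They will be asked to notify the study staff for persistent low blood sugar". That request also covers persistent highs and ketones and has no end date. Section 13.1 has a request without an end date on highs: "Subjects will be advised to contact the study team for persistent hyperglycemia and/or presence of urine ketones". The same section limits two others to treatment: "They will be asked to contact the study team for persistent hypoglycemia while taking liraglutide" and "While taking liraglutide, the subjects will be counseled to notify study staff if they develop severe abdominal pain".

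**The concern.** The plan itself names two opposite risks in section 13.1: lows from adding a GLP-1 analogue to insulin, and highs or ketonuria from cutting insulin. Its protection against lows is the insulin reduction during the treatment week. After the final dose the subject reverses that reduction at home, at a time of his or her choosing within 48 hours, with no planned diary, call or download.

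Hypoglycemia rates and pancreatitis are safety endpoints (section 7.1), and pancreatitis is the only stated trigger for suspending the research (section 11.8). A subject who has handed back the pen could reasonably think that the abdominal pain instruction has lapsed. Exploratory Aim 1 describes the side-effect profile by type, number and rate, and a late effect of the supervised final dose has no planned place in that record. What is at stake is the completeness of safety data in a small study that includes minors and may inform longer trials.

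**Working it through.** **The plan's one computed figure.** Section 10.2 gives 9 subjects for a change of 22 mg/dL with SD 20, 80% power and alpha 0.05, by paired t-test. The effect size is 22/20 = 1.10. Taking the test as two-sided, which the plan does not state, exact power is 0.761 at n = 8 and 0.823 at n = 9, so 9 is reproduced. The endpoint compares mean glucose over the 7 days before and the 7 days after liraglutide is started. Nothing after Day 14 enters it, so this point leaves the figure alone.

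**How long the final dose is observed.** Dosing is 45 minutes before the meal test and sampling runs for 3 hours: 0.75 + 3 = 3.75 hours. Scheduled observation after that dose ends at about that point.

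**Size of the insulin change made afterwards.** Section 8.2 (Visit 2) cuts basal rates by 25% and meal boluses by 33%. Section 13.1 gives 25% and 30%. Undoing a cut of fraction c raises the setting by 1/(1 − c) − 1:

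| Setting | Cut | Rise on restoration |
|---|---|---|
| Basal (both sections) | 25% | 1/0.75 − 1 = 33% |
| Bolus (13.1) | 30% | 1/0.70 − 1 = 43% |
| Bolus (8.2) | 33% | 1/0.67 − 1 = 49% |

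Section 13.1 allows insulin to be raised during the treatment week for persistent highs or ketones. For such a subject the rise is smaller, down to 0% if previous settings were already back in place.

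**What covers the period after Visit 3.**

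| Route | Where | Scheduled after Day 14? |
|---|---|---|
| Visit, call, diary or CGM download | 6.1, 8.2, 8.6 | No |
| Contact details for any problem | 8.2 Visit 2, 8.3 | No; subject-initiated, no end date |
| Request to report lows, highs, ketones | 8.2 Visit 2 | No; subject-initiated, no end date |
| Request on highs and ketones | 13.1 | No; subject-initiated, no end date |
| Request on lows | 13.1 | No; worded for the time on drug |
| Severe abdominal pain | 13.1 | No; worded for the time on drug |
| Pump and meter downloads, record access | 10.5, 13.1, 24.3 | No; incidental to clinic care or data verification |

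**When a follow-up call should fall.** A subject who uses the full 48 hours resumes on Day 16 at about the clock time at which Visit 3 ended. A Day 17 call made before that clock time leaves less than 24 hours on restored settings. A diary kept to the end of Day 17 gives at least 24 hours, because the latest possible resumption is the end of Day 16. A Day 18 call can collect all of it.

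**The case against.** The strongest reply is that the period is not uncovered. Subjects leave Visit 2 with contact details for any problem and a request to report persistent lows, highs and ketones, neither of which expires. Abdominal pain is plainly a problem, and reading the treatment-bound wording as ending when the pen is returned, hours after a dose of a long-acting drug, is literal-minded. All subjects attend the same clinic, all use pumps, downloads are scanned into the chart, and the team may consult that chart. The insulin change only returns subjects to their own usual settings, after staff have reviewed those settings. No aim or endpoint defines a post-treatment period.

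Most of this stands, and it bounds the point. A reader might infer that later events are known only if subjects volunteer them unprompted, or that no record exists. The documents do not support either reading: the Visit 2 instructions are a prompt, and clinic records could later reveal events. A reader might also want to put hours on the overlap between restored insulin and remaining drug action. The documents give no duration of action, so no such figure can be supported.

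What the reply does not remove is the absence of any scheduled collection, and the disagreement between sections on whether lows and abdominal pain are still to be reported once treatment has ended.

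**Conclusion.** The point holds as a minor, optional improvement. Followed as written, the plan leaves the end of the last dose and the return to previous insulin settings (nominally +33% basal and +43% to +49% bolus, possibly as little as 0%) without a scheduled safety check in up to 12 subjects, so events there may be missed. The percentages describe a change in pump settings back to the subject's own earlier values. They are not a measured risk or a rise above usual insulin.

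It would be wrong to read this as a flaw in the efficacy result: the primary endpoint, the sample size and the treatment-week rates are unaffected.

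The conclusion assumes that no later contact is specified elsewhere. The data collection tool and the consent and assent forms were not available for review, so an instruction given only there cannot be excluded. Even so, section 8.2 is where safety-monitoring procedures are meant to be described.

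**What to change.** - **Section 8.2, Visit 3:** have subjects continue the existing diary from the end of Visit 3 through Day 17.
- **Sections 8.2 and 13.1:** state that the instructions on low glucose, high glucose, ketones and severe abdominal pain apply until the follow-up call.
- **Follow-up:** existing staff make one telephone call on Day 18 to collect diary events and the date on which previous settings were resumed.
- **Reporting:** present these events separately as a post-treatment period, so that the treatment-week rates keep their meaning.

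The Visit 3 dose and the 48-hour advice stay as they are. The call records events after the fact; protection during the period comes from the extended reporting instructions.

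Cost: up to 12 calls, and 3 to 4 extra diary days per subject (the rest of Day 14 plus Days 15 to 17), at most about 12 × 4 = 48 in all. Section 6.1 changes from two weeks to about 18 days, and the consent and assent forms need matching text.
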